### 9.4 Populations for Analysis

The primary analysis population will be the Intent-to-Treat (ITT) cohort which includes all enrolled subjects.

### 9.5 Handling of Dropouts or Missing Data

No imputation of or adjustments for missing data will be performed for the primary analyses. All available data will be presented. For time to event analyses, subjects who do not experience the event in question will be censored at their last known follow-up.

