### 7.9.1 When and How to Withdraw Subjects

Subjects may be withdrawn at the medical discretion of the physician, or they may voluntarily withdraw their consent at any time without impact to their medical treatment.

	No.: CP 65007	REV. C
	TITLE: Disrupt PAD BTK II Study	
	CLASS: CLINICAL PROTOCOL	PAGE 37 OF 71

Prior to enrollment, the investigative site should provide contact information and detailed instructions to subjects on how to withdraw from the study. When a subject is withdrawn, all data obtained prior to the time of withdrawal may be submitted to the Study Sponsor and be included in the study database, unless otherwise requested by the subject in writing.

In the event a subject is lost to follow-up or cannot be contacted for post-treatment assessments, at least three attempts (two phone calls and a certified letter) will be made to locate the study subject, and these efforts will be documented. If the subject cannot be located, the subject's lost to follow-up status will be documented in the EDC and they will be exited from the clinical study.

Should the subject expire, an adverse event form and a study exit/withdrawal form must be completed. Physician assessment is required to determine if the cause of death was possibly, probably, or definitely related to the IVL System. If available, copies of the death certificate and/or an autopsy report should be included in the research records. The Investigator may need to provide written notification to the IRB/EC upon the death of the study subject, dependent on the IRB/EC policies.

	No.: CP 65007	REV. C
	TITLE: Disrupt PAD BTK II Study	
	CLASS: CLINICAL PROTOCOL	PAGE 38 OF 71

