### 9.1 General Statistical Methods

Descriptive statistics will be provided in this clinical study. Analyses will be conducted at pre-specified time points including 30 days, 6, 12 and 24 months.

Categorical variables will be summarized by the number of observations available, frequency, and percentage. Unless otherwise noted, missing data will be excluded from the denominator. Comparisons will utilize a Chi-square test, or Fisher's exact test when 20% or more of expected cell frequencies are less than 5. Clinical outcomes analyzed at 30 days will be evaluated as categorical (binary) data. McNemar's chi-square may be used to assess within-subject changes in a bivariate response variable. Exact confidence intervals will be generated for estimates of proportions.

Continuous variables will be summarized by the mean, standard deviation, median, minimum, and maximum. Within-subject changes will be analyzed parametrically using the Paired t-test if the differences are normally distributed, or non-parametrically using the Sign-Rank Test if the differences are not normally distributed. Asymptotic confidence intervals will be generated for estimates of means.

Exploratory analyses and clarifications to the protocol specified analysis plan will be documented in the SAP. Statistical analyses will be performed using SAS System® Version 9.4 or higher.

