### 9.3 Sample Size Determination

The sample size was calculated based on the precision of the exact 2-sided 95% confidence interval (CI) of the primary effectiveness endpoint, using the LIBERTY 360 study results as a reference. The LIBERTY 360 study of endovascular interventions for PAD is one of the largest, real-world, core laboratory–adjudicated studies to include patients with varying degrees of PAD severity. Procedural Success for the RC 4-5 cohort of this large contemporary data set was 75.8% [71.9, 79.3] [20].

The calculation of the Disrupt PAD BTK II sample size was based on a procedural success estimate of 75.8%. Combined with a desired precision of +/- 5.8% and an alpha of 0.05 (95% CI), a sample size of 225 was selected to provide a probability width (“power”) of 0.827. Assuming a lost-to-follow-up rate of 10%, up to 250 subjects will be enrolled.

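### Censoring deaths under section 9.5 makes 6-, 12- and 24-month CD-TLR and major amputation rates exceed the share of subjects who have the event; add a cumulative incidence estimate

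*Combined protocol and SAP*

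**What the plan says.** Section 5.2 lists CD-TLR and major target limb amputation as secondary endpoints at 30 days and at 6, 12 and 24 months. It names no estimator for either.

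Section 9.1 sets the analysis times: "Analyses will be conducted at pre-specified time points including 30 days, 6, 12 and 24 months". It fixes the data type at the first of them only: "Clinical outcomes analyzed at 30 days will be evaluated as categorical (binary) data". For categorical summaries it adds: "Unless otherwise noted, missing data will be excluded from the denominator".

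Section 9.5 gives the rule for the other kind of analysis: "For time to event analyses, subjects who do not experience the event in question will be censored at their last known follow-up". It does not list the endpoints it governs, and it does not separate death from other reasons for the end of follow-up.

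Death ends participation under section 7.9.1: "Should the subject expire, an adverse event form and a study exit/withdrawal form must be completed". Section 9.4 defines the population: "The primary analysis population will be the Intent-to-Treat (ITT) cohort which includes all enrolled subjects". Section 9.1 also defers detail: "Exploratory analyses and clarifications to the protocol specified analysis plan will be documented in the SAP". The supplied text holds no analysis rules beyond section 9. It mentions neither cumulative incidence nor competing risks.

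**The concern.** A subject who dies without a revascularization or amputation cannot have one later. Censoring at death treats that subject as still able to have the event, at the same rate as the survivors. One minus Kaplan-Meier then answers a hypothetical question: how many would have the event if nobody died. It is a legitimate quantity, but it is not the share of treated subjects who have the event, and many readers of a 24-month rate will take it for that share.

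Section 3.2 presents long-term follow-up as something this study adds to the earlier BTK study, and 24 months is where the gap is widest. The direction is against the device: reported event rates would be higher than the share of subjects affected. A single-arm descriptive study has no comparator in which the same effect would partly cancel.

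**Working it through.** **Plan's own figure.** There is none on this point: the documents give no expected rate for CD-TLR, amputation or death. The only related input is section 9.3: "Assuming a lost-to-follow-up rate of 10%, up to 250 subjects will be enrolled". That reproduces as 225/0.90 = 250. I use 225 below only to scale the sampling error.

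**Assumptions.** Constant hazards over 24 months; one minus Kaplan-Meier (1−KM) of 20.0% at 24 months; mortality of 5%, 10%, 20% and 30% over 24 months; no other losses. The eligibility requirement of life expectancy over one year may keep mortality toward the low end.

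**Formulas.** With cumulative 24-month hazards a for the event and d for death:

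- a = −ln(1 − 0.20) = 0.2231; d = −ln(1 − mortality)
- share with the event (cumulative incidence, CIF) = a/(a+d) × (1 − exp(−(a+d)))
- event-free deaths (EFD) = d/(a+d) × (1 − exp(−(a+d)))
- proportion if event-free deaths are dropped = CIF/(1 − EFD)

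At 20% mortality, d = 0.2231 and exp(−(a+d)) = 0.8 × 0.8 = 0.64. So CIF = 0.5 × 0.36 = 18.0%, EFD = 18.0%, and the dropped-deaths proportion = 0.18/0.82 = 22.0%.

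| Mortality at 24 months | 1−KM, deaths censored | Share with event | Excess of 1−KM (points) | EFD | Proportion, deaths dropped |
|---|---|---|---|---|---|
| 5% | 20.0% | 19.5% | 0.5 | 4.5% | 20.4% |
| 10% | 20.0% | 19.0% | 1.0 | 9.0% | 20.9% |
| 20% | 20.0% | 18.0% | 2.0 | 18.0% | 22.0% |
| 30% | 20.0% | 16.9% | 3.1 | 27.1% | 23.2% |

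**Earlier time.** At 12 months, with half the cumulative hazards, 1−KM is 10.6%. The share is 10.3%, 10.0% and 9.7% for 24-month mortality of 10%, 20% and 30%.

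**Rarer event.** With 1−KM of 5.0% at 24 months, the share is 4.9% at 5% mortality and 4.2% at 30%.

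**Check with other assumed rates.** With annual risks of 10% for the event and 10% for death, the 24-month share is 17.2%, 1−KM is 19.0% and the dropped-deaths proportion is 20.8%. A simulation of 4,000 cohorts of 250 gave the same three figures, and 1−KM was never below the share.

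**If section 9.1 governed instead.** With 225 subjects and 20% mortality, there would be 40.5 expected events and 40.5 expected event-free deaths. Keeping the deaths in the denominator gives 40.5/225 = 18.0%, the share itself. Dropping them gives 40.5/184.5 = 22.0%. The result therefore turns on whether an event-free death counts as missing, which the text does not say.

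**Scale.** The 95% half-width at 20% and n = 225 is 1.96 × √(0.2 × 0.8/225) = 5.2 points.

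**The case against.** The strongest case against is that censoring at death is common, that the plan refers clarifications to a SAP not fully in hand, and that the shifts are small. Most of this stands. Kaplan-Meier is not an error, so the remedy keeps it. The SAP may already settle the matter, so the documents cannot show that an estimator would be chosen after the data are seen. At 5% to 10% mortality the excess is 1 point or less. What survives is that the one censoring rule in writing, followed as it stands, yields a rate above the share of subjects affected. That excess is systematic and does not shrink with more subjects.

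Three stronger readings are tempting and are not supported.

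- A reader might infer that both written rules inflate the rates. Section 9.1 excludes missing data, but nothing calls an event-free death missing. Such a subject's status is known, and section 9.4 analyses everyone enrolled. The 22.0% figure applies only under a reading the text does not state.
- A reader might infer that sections 9.1 and 9.5 compete equally for the later time points. Because only 30-day outcomes are made binary, and the censoring rule would otherwise have little to apply to, section 9.5 is the natural reading, though it is never stated.
- A reader might infer that a limb amputated above the ankle always leaves the patency denominator. Target lesions may lie as high as the distal popliteal segment, so a proximal lesion can remain and be scanned by duplex ultrasound (DUS).

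**Conclusion.** The point holds as a minor improvement to the method. Under the natural reading of section 9.5, 24-month CD-TLR and major amputation rates would exceed the share of subjects with the event. For an assumed 1−KM of 20.0%, the excess is 0.5 to 3.1 points across 5% to 30% mortality; it is smaller at earlier times and for rarer events. The sizes rest on assumed rates, constant hazards and no other losses. The direction needs only that some subjects die event-free before later events occur.

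Every gap between 1−KM and the share shown here is below the 5.2-point half-width. Both primary endpoints and the sample size are unaffected, and no formal hypothesis test is planned for these endpoints.

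**What to change.** In section 9.5 or the SAP:

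1. State that CD-TLR and major target limb amputation at 6, 12 and 24 months are reported by the Aalen-Johansen cumulative incidence, with death as a competing event, beside the Kaplan-Meier estimate.
2. State that event-free deaths stay in the denominator, as non-events, of any proportion reported for these endpoints.

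The cost is a few sentences and a few lines of code. Deaths and amputations are already collected, so no new data are needed. The downside is one extra estimate per endpoint to present and explain.

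Optional and separate: add a patency sensitivity rate that counts major target limb amputation as loss of patency where the amputation leaves the target lesion without an evaluable DUS, and report the number affected. Whether amputation is loss of patency is a convention, so this would supplement the defined endpoint and not replace it.

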### 5.2 Secondary Endpoints

- Serious angiographic complications (flow-limiting dissection, perforation, distal embolization, or acute vessel closure) as assessed by the angiographic core lab
- Lesion Success defined as final residual stenosis  $\leq 50\%$  in the target lesion without serious angiographic complications as assessed by the angiographic core lab
- Primary Patency at 6 and 12 months as assessed by both subject and lesion level defined as the absence of both total occlusion (100% diameter stenosis as assessed by DUS core lab) in all of the target lesions in a flow pathway, as well as any CEC adjudicated Clinically-Driven Target Lesion Revascularization (CD-TLR)
- Clinically-Driven Target Lesion Revascularization (CD-TLR), CEC adjudicated, at 30 days, 6, 12, & 24 months
- Major Adverse Events (MAE), CEC adjudicated, at 30 days defined as a composite of:
  - Need for emergency surgical revascularization of target limb
  - Unplanned target limb major amputation (above the ankle)
  - Symptomatic thrombus or distal emboli that require surgical, mechanical, or pharmacologic means to improve flow, and extend hospitalization

	No.: CP 65007	REV. C
	TITLE: Disrupt PAD BTK II Study	
	CLASS: CLINICAL PROTOCOL	PAGE 20 OF 71

- Perforations that require an intervention, including bail-out stenting
- Quality of Life (QoL) assessed by VascuQoL questionnaire at 30 days, 6, 12, & 24 months, reported as change from baseline
- Major Target Limb Amputation, CEC adjudicated, at 30 days, 6, 12, & 24 months
- Ankle-brachial index (ABI) or toe-brachial index (TBI) at 30 days, 6, 12, & 24 months, reported as change from baseline
- Rutherford Category at 30 days, 6, 12, & 24 months, reported as change from baseline
- Number of existing, new, and recurrent wounds at 30 days, 6, 12, & 24 months
- Number of healed wounds at 30 days, 6, 12, & 24 months
- Number of non-healed wounds by category (improving, stagnant, worsening) at 30 days, 6, 12, & 24 months

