### 15.1 Study Definitions

**Abrupt or Acute Closure:** Angiographic documentation of significantly reduced flow due to mechanical dissection, thrombus, or severe vessel spasm in the treatment area.

**Acute Limb Ischemia:** A sudden decrease in limb perfusion that causes a potential threat to limb viability (manifested by ischemic rest pain, ischemic ulcers, and/or gangrene) in patients who present within two weeks of the acute event.

**Adverse Device Effect (ADE):** Adverse event related to the use of an investigational medical device.

*Note: This definition includes adverse events resulting from insufficient or inadequate instructions for use, deployment, implantation, installation, or operation, or any malfunction of the investigational medical device.*

*Note: This definition includes any event resulting from use error or from intentional misuse of the investigational medical device.*

*Note: This includes “comparator” if the comparator is a medical device.*

**Adverse Event (AE):** Untoward medical occurrence, unintended disease or injury, or untoward clinical signs (including abnormal laboratory findings) in subjects, users or other persons, whether or not related to the investigational medical device and whether anticipated or unanticipated.

*Note: This definition includes events related to the investigational medical device or the comparator.*

*Note: This definition includes events related to the procedures involved.*

*Note: For users or other persons, this definition is restricted to events related to the use of investigational medical devices or comparators.*

**Amputation (major):** Any requirement for amputation above the ankle.

**Amputation (minor):** Any requirement for amputation below the ankle.

**Amputation, Unplanned:** An amputation associated with the target limb that occurs between the index procedure and 30 days post-procedure that was not previously planned as part of the overall treatment strategy.

**Ankle-Brachial Index (ABI):** The ratio of systolic blood pressure measured at the ankle to systolic blood pressure measured at the brachial artery.

**Below the Knee (Lesion Location):** From center of knee joint space to ankle joint.

**Calcification Classification (PARC):** Calcification will be assessed by the angiographic core lab according to the Peripheral Academic Research Consortium (PARC) definition [21].

	No.: CP 65007	REV. C
	TITLE: Disrupt PAD BTK II Study	
	CLASS: CLINICAL PROTOCOL	

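### The plan has no rule for limb loss in the patency and CD-TLR analyses, and by default an amputee with no scan leaves the patency denominator

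*Combined protocol and SAP*

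**What the plan says.** **Endpoints.** Section 5.2 bases primary patency at 6 and 12 months on "absence of both total occlusion (100% diameter stenosis as assessed by DUS core lab) in all of the target lesions" of a flow pathway, together with freedom from CD-TLR. CD-TLR is also an endpoint of its own: "Clinically-Driven Target Lesion Revascularization (CD-TLR), CEC adjudicated, at 30 days, 6, 12, & 24 months". Section 15.1 defines it as a repeat procedure on the target lesion, done for a stenosis of at least half the diameter plus ischaemia or a return of the presenting syndrome. Amputation is part of neither definition.

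**Where amputation is counted.** Section 15.1 defines major amputation as "Any requirement for amputation above the ankle". It is a separate secondary endpoint, adjudicated by the events committee, at the same four time points as CD-TLR. It is also part of the 30-day primary safety composite and, if unplanned, of the 30-day MAE composite.

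**Analysis rules.** Section 9.1: "Unless otherwise noted, missing data will be excluded from the denominator". Also in 9.1: "Clinical outcomes analyzed at 30 days will be evaluated as categorical (binary) data"; no method is given for the later time points. Section 9.5: "No imputation of or adjustments for missing data will be performed for the primary analyses", and "For time to event analyses, subjects who do not experience the event in question will be censored at their last known follow-up". It does not say which endpoints are analysed as time to event. Section 9.1 leaves further clarification to a SAP, but the text supplied contains no rule on amputation. By contrast, section 7.6 gives wounds their own amputated status at follow-up.

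**The concern.** Target lesions lie between the P3 segment and the ankle (section 7.2.1). An above-ankle amputation will therefore usually remove the lesion or leave nothing useful to scan. That is an inference from anatomy; a proximal lesion may survive a below-knee amputation. The open list of withdrawal reasons in section 7.9 does not include amputation, so the subject can stay in the study with no readable duplex result.

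Such a scan is missing because of the outcome. Dropping the subject assumes that limbs lost would have been patent as often as limbs kept. Section 6.7 caps RC 3 at 20%, so at least 80% of subjects are RC 4 or 5, the group in which limb loss matters most. Planned major amputation is an exclusion (section 7.2.2), so those that occur are follow-up outcomes.

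Patency and CD-TLR are the study's durability results. Amputation can also take the place of re-treatment, so a low CD-TLR rate need not mean a durable result.

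**Working it through.** **1. Plan's own figures.** There are none to reproduce: the documents state no patency, CD-TLR or amputation rate. Section 9.3 concerns procedure success. Only its enrolment is used here, 225 / (1 − 0.10) = 250, and the percentages in steps 3, 4 and 6 do not depend on it.

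**2. What the written rules do with an amputee.**

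| Before the amputation | Patency (9.1) | CD-TLR |
|---|---|---|
| CD-TLR | failure | event |
| Occlusion on duplex | failure at that visit; carrying it to a later visit is not spelled out | no event |
| Neither, and no scan afterwards | excluded | no event |

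The third row is the gap.

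**3. Size for patency.** All rates are assumptions: CD-TLR 10%, occlusion without CD-TLR 15%, so other failures f = 25%. Major amputation a = 3% to 8%, all in the third row.

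- Excluded: (1 − f − a) / (1 − a). Counted as failure: 1 − f − a.
- a = 3%: (250 − 62.5 − 7.5) / (250 − 7.5) = 180 / 242.5 = 74.2%, against 180 / 250 = 72.0%. Gap 2.2 points.
- a = 8%: (250 − 62.5 − 20) / (250 − 20) = 167.5 / 230 = 72.8%, against 167.5 / 250 = 67.0%. Gap 5.8 points.

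**4. Sensitivity.**

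- If half the amputees had already failed and sit within the 25%, only 1.5% to 4% are excluded. Then 0.735 / 0.985 = 74.6% against 73.5% (1.1 points), and 0.71 / 0.96 = 74.0% against 71.0% (3.0 points).
- Wider assumptions, with 225 subjects in whole numbers, amputation 2% to 10% (4 to 22 subjects) and other failures 15% or 25% (34 or 56 subjects). The smallest gap is 165/221 − 165/225 = 1.3 points. The largest is 169/203 − 169/225 = 8.1 points.

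**5. Is the CD-TLR figure distorted?** Assume constant hazards over 24 months, CD-TLR 10% and amputation 5%. Cumulative hazards are −ln 0.90 = 0.1054 and −ln 0.95 = 0.0513.

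- Amputation as a competing event: 0.1054 / (0.1054 + 0.0513) × (1 − 0.90 × 0.95) = 9.75%, so 90.2% are free of CD-TLR.
- Amputees kept at risk as event-free to 24 months: also 90.2%.
- Censored at amputation: 90.0%.

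Across amputation of 2% to 10% and CD-TLR of 10% to 20%, keeping amputees at risk differs from censoring them by at most 1 point (81.0% against 80.0%).

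**6. What separate reporting gives.** With CD-TLR rate t and amputation rate a, the share with either lies between max(t, a) and t + a. For t = 10% and a = 8% that is 10% to 18%, so limb kept without CD-TLR is anywhere from 82% to 90%. For a = 3% it is 87% to 90%.

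**The case against.** The case for leaving the plan alone is substantial. Patency is an anatomical endpoint and CD-TLR a procedural one; neither claims to measure limb salvage. Amputation is adjudicated and reported at the same time points, and within the primary safety composite. The study is descriptive, so no success decision rests on either rate. The SAP may hold a rule that is not in the text supplied. Death raises the same question and is equally unaddressed.

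Most of this stands. It argues for keeping both definitions and for a low severity. It does not repair the patency denominator: a separate amputation rate does not show how many amputees were left out of patency, and two marginal rates only bound the joint result.

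A reader might infer something stronger: that section 9.5 carries every amputee as patent and free of CD-TLR to the last visit, so that limb loss never counts and both endpoints are overstated by up to 8 points. The documents do not support this:

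- Section 9.5 names no endpoint, and no section carries patency forward. The written rule for a missing categorical result is exclusion.
- An occlusion or CD-TLR recorded before the amputation is still a failure.
- Setting 90% free of CD-TLR against 82% to 87% free of CD-TLR with the limb kept compares two different endpoints. It is not an error in the first.
- Treating amputation as a competing event gives essentially the same CD-TLR figure as keeping amputees at risk (step 5), so it remedies nothing.

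**Conclusion.** The point holds in a limited form. Major target limb amputation has no rule in either analysis, and the written default excludes an amputee with no scan and no earlier CD-TLR from patency. That exclusion depends on the outcome and biases patency upward. On assumed rates of 3% to 8% amputation and 25% other failures the gap is 2.2 to 5.8 points. It rests on every amputee having no scan and no earlier failure, and falls to 1.1 to 3.0 points if half had already failed.

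The CD-TLR rate is correct for what it measures. It should not be read as durability without limb loss, because the joint outcome cannot be recovered from the separate rates. Severity is low: both are secondary endpoints without formal testing.

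**What to change.** Keep both endpoint definitions. In section 9.5 or the SAP:

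- (a) Add a pre-specified supplementary patency analysis at 6 and 12 months in which an adjudicated major amputation of the target limb, without earlier failure, counts as a failure. State how many amputees the main analysis excludes.
- (b) Beside CD-TLR at 6, 12 and 24 months, report the composite of CD-TLR or major target limb amputation, with component counts.

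No competing-event change to the CD-TLR analysis is needed.

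The cost is a few sentences and two extra table entries, since amputations are already collected and adjudicated at these time points. The downside is that the added figures will be lower, and that an amputation with an open artery counts as a failure in the supplementary analysis. The component counts make that visible.
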